### 6.2.3 Restricted concomitant medications

### Restricted concomitant medications

Medication/class of drug:	Usage (including limits for duration permitted and special situations in which it's allowed ):

Strong CYP3A inhibitors:            itraconazole, telithromycin, clarithromycin, boosted protease inhibitors, indinavir, saquinavir, nelfinavir, boceprevir, telaprevir
 
Moderate CYP3A inhibitors:            ciprofloxacin, erythromycin, diltiazem, fluconazole, verapamil
	
Strong or moderate CYP3A inhibitors should be avoided with olaparib. If there is no suitable alternative concomitant medication then the dose of olaparib should be reduced for the period of concomitant administration. The dose reduction of olaparib should be recorded in the CRF with the reason documented as concomitant CYP3A inhibitor use.
 
 
• Strong CYP3A inhibitors – reduce the dose of olaparib to 100 mg twice daily for the duration of concomitant therapy with the strong inhibitor and for 5 half lives afterwards.
 
• Moderate CYP3A inhibitors - reduce the dose of olaparib to 150 mg twice daily for the duration of concomitant therapy with the moderate inhibitor and for 3 half lives afterwards.
 
• After the washout of the inhibitor is complete, the olaparib dose can be re-escalated.
 

Strong inducers:            phenobarbital, phenytoin, rifampicin, rifabutin, rifapentine, carbamazepine, nevirapine, enzalutamide and St John's Wort
 
Moderate CYP3A inducers:            bosentan, efavirenz and modafinil
	
Strong or moderate CYP3A inducers should not be taken with olaparib. If the use of any strong or moderate CYP3A inducers are considered necessary for the patient's safety and welfare this could diminish the clinical efficacy of olaparib. If a patient requires use of a strong or moderate CYP3A inducer then they must be monitored carefully for any change in efficacy of olaparib.

### Restricted concomitant medications

Medication/class of drug:	Usage (including limits for duration permitted and special situations in which it's allowed):

 
• CYP3A4 substrates: hormonal contraceptive, simvastatin, cisapride, cyclosporine, ergot alkaloids, fentanyl, pimozide, sirolimus, tacrolimus and quetiapine
 
• CYP2B6 substrates: bupropion, efavirenz
 
• OATP1B1 substrates: bosentan, glibenclamide, repaglinide, statins and valsartan
 
• OCT1, MATE1 and MATE2K substrates: metformin
 
• OCT2 substrates: serum creatinine
 
• OAT3 substrates: furosemide, methotrexate
 
	
Effect of olaparib on other drugs:
 
 
• Based on limited in vitro data, olaparib may increase the exposure to substrates of CYP3A4, OATP1B1, OCT1, OCT2, OAT3, MATE1 and MATE2K.
 
• Based on limited in vitro data, olaparib may reduce the exposure to substrates of 2B6.
 
• Caution should be observed if substrates of these isoenzymes or transporter proteins are co-administered.
 

Anticoagulant therapy
	
Patients who are taking warfarin may participate in this trial; however, it is recommended that international normalized ratio (INR) be monitored carefully at least once per week for the first month, then monthly if the INR is stable. Subcutaneous heparin and low molecular weight heparin are permitted.

Palliative radiotherapy
	
Palliative radiotherapy may be used for the treatment of pain at the site of bony metastases that were present at baseline only after completion of the Cycle 6 response assessment, provided the investigator does not feel that these are indicative of clinical disease progression during the study period. Study treatment should be discontinued for a minimum of 3 days before a patient undergoes therapeutic palliative radiation treatment. Study treatment should be restarted within 4 weeks as long as any bone marrow toxicity has recovered.

### Restricted concomitant medications

Medication/class of drug:	Usage (including limits for duration permitted and special situations in which it's allowed):
Administration of other anti-cancer agents	Patients must not receive any other concurrent anti-cancer therapy, including investigational agents, while on study treatment. Patients may use hydroxyurea, as outlined in the inclusion criteria, for leukocytosis. While not standard therapy for patients with AML or MDS, Patients may continue the use of bisphosphonates if they are already on these therapies. Low dose corticosteroids may also be used for any chronic condition provided the dose is stable during the study and they were started at least 4 weeks prior to beginning study treatment.

### 6.3 Duration of Therapy

In the absence of treatment delays due to AE(s), treatment may continue until one of the following criteria applies:

- Disease progression
- Intercurrent illness that prevents further administration of treatment
- Unacceptable AE(s)
- Patient decides to withdraw from the study
- General or specific changes in the patient's condition render the patient unacceptable for further treatment in the judgment of the investigator
- Clinical progression
- In patients without prior exposure to IDH inhibitors: the absence of CR/CRh/mCR
- Patient non-compliance
- Pregnancy
  - All women of child-bearing potential should be instructed to contact the investigator immediately if they suspect they might be pregnant (*e.g.*, missed or late menstrual period) at any time during study participation.
  - The investigator must immediately notify CTEP in the event of a confirmed pregnancy in a patient participating in the study.
- Termination of the study by sponsor
- The drug manufacturer can no longer provide the study agent

The reason(s) for protocol therapy discontinuation, the reason(s) for study removal, and the corresponding dates must be documented in the Case Report Form (CRF).

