### **1.2 Secondary Objectives**

- 1.2.1 To determine the overall response rate (ORR) to olaparib using a composite ORR endpoint (CR + morphologic leukemia-free state [MLFS] + partial response [PR]) in patients with IDH mutant AML or MDS treated with olaparib.
- 1.2.2 To establish the progression free survival (PFS) of patients with IDH mutant AML or MDS treated with olaparib.
- 1.2.3 To determine the overall survival (OS) of patients with IDH mutant AML or MDS treated with olaparib.
- 1.2.4 To establish the duration of response (DOR) to treatment with olaparib.
- 1.2.5 To evaluate the safety and tolerability of olaparib in AML or MDS patients.

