#### 9.1.2.1 Efficacy Evaluation

Clinical efficacy will be evaluated by MDS International Working Group (IWG) 2006 criteria (Cheson *et al.*, 2006) and AML IWG 2003 criteria (Cheson *et al.*, 2003) after 6 cycles of treatment. The primary endpoint will be cumulative composite CR (CR, CRi, CRh) and we will also record the cumulative ORR will include complete remission (CR), complete remission with incomplete blood count recovery (CRi), partial response (PR), and bone marrow complete remission (marrow CR/MLFS) achieved at least at one point during these 6 cycles.

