#### 9.4.2 Evaluation of Objective Response Rate

The effectiveness of the drug in patients for each cohort will be independently assessed by composite CR rate (CR+CRi+CRh). Objective Response Rate (ORR) will be included as a secondary endpoint, calculated as a composite CR+MLFS+PR. The exact two-sided 95% confidence intervals for the ORR will be reported. For lifetime data analyses, e.g., overall and progression free survival, the study survival will be estimated using the Kaplan-Meier method with the 95% confidence intervals (CIs). The CI based on the Greenwoods variance will be reported. In addition, the possible risk factors will be compared for survival with log-rank test. For multivariate analysis, the proportional hazards Cox model will be applied to investigate potential prognostic factors, such as age and stage of disease on the survival data. The adjusted p-values of the odds ratios and the adjusted 95% confidence interval will be reported.

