## 12. MEASUREMENT OF EFFECT

### 12.1 Antitumor Effect – Hematologic Tumors

For patients not previously exposed to IDH inhibitors, response is assessed after cycles 1, 3, 6, 9, and 12 for the first year. For patients *with* prior IDH inhibitor exposure, response is assessed after cycles 3, 6, 9, and 12 for the first year on treatment.

Category	Definition	Comment
Complete Response (CR)	Bone marrow blasts <5%; absence of circulating blasts and blasts with Auer rods; absence of extramedullary disease; ANC $\geq 1.0 \times 10^9/L$ (1,000/mcL); platelet count $\geq 100 \times 10^9/L$ (100,000/mcL)*	
CR with incomplete hematologic recovery (CRi)/CRh	All CR criteria except for residual neutropenia ( $<1.0 \times 10^9/L$ [1,000/mcL]) or thrombocytopenia ( $<100 \times 10^9/L$ [100,000/mcL])* CRh: complete remission with partial hematological recovery (platelets > 50,000 mcL and ANC > 500/mcL)	
Morphologic leukemia-free state (“marrow CR”, MLFS)	Bone marrow blasts <5%; absence of blasts with Auer rods; absence of extramedullary disease; no hematologic recovery required	Marrow should not merely be aplastic—at least 200 cells should be enumerated, or cellularity should be at least 10%
Partial response (PR)	All hematologic criteria of CR; decrease of bone marrow blast percentage to between 5% and 25%; and decrease of pretreatment bone marrow blast percentage by at least 50%	Especially important in the context of phase 1-2 clinical trials
Stable disease (SD)	Absence of CR, CRi, PR, MLFS; and criteria for PD not met	The period of stable disease should last at least 3 months

Category	Definition	Comment

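### The stopping rule for IDH-inhibitor-naive patients takes a partial responder off olaparib for lack of response and leaves CRi to the site's labelling, which affects DOR and PFS in arms 1 and 3

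*Combined protocol and SAP*

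**What the plan says.** Section 6.3 (Duration of Therapy) says that "treatment may continue until one of the following criteria applies". One item applies only to arms 1 and 3: "In patients without prior exposure to IDH inhibitors: the absence of CR/CRh/mCR". It gives no cycle or assessment at which it takes effect, and it has no counterpart for IDH-inhibitor-exposed patients (arms 2 and 4).

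The endpoints use different lists:

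- Primary endpoint, Section 9.1.2.1: "The primary endpoint will be cumulative composite CR (CR, CRi, CRh").
- ORR, Section 9.4.2: "calculated as a composite CR+MLFS+PR". Section 1.2.1 gives the same composite. Section 9.1.2.1 lists CR, CRi, PR and "bone marrow complete remission (marrow CR/MLFS"), counted if "achieved at least at one point during these 6 cycles".
- Stable disease, Section 12.1: "Absence of CR, CRi, PR, MLFS; and criteria for PD not met". This row treats CRi, PR and MLFS as separate states, none of which is stable disease.

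Two other places bear on when a naive patient leaves treatment. Section 2.3 describes close monitoring so that naive patients can move to standard care in the case of progression. The progressive-disease row of Section 12.1 allows patients with PD to stay on study, after discussion with the PI, if they are judged to be benefiting.

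**The concern.** The response states that keep a naive patient on treatment are not the states that the analysis counts as response. PR is an ORR success and is missing from the Section 6.3 list. CRi is a primary-endpoint success and is not named there either.

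The matter is statistical as well as editorial. A responder who stops because of this item leaves the schedule on which progression is documented. DOR and PFS (Section 9.4.3) run to documented progression, death or last follow-up, and nothing there covers a responder whom the protocol itself took off drug. Arms 1 and 3 would then contain a group of responders whose DOR and PFS partly reflect the stopping rule.

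**Working it through.** **Step 1. Compare each response state with the Section 6.3 list.** Definitions are from Section 12.1.

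| State | Marrow blasts | Blood counts | Counts toward | Named in 6.3? |
|---|---|---|---|---|
| CR | <5% | ANC at least 1,000/mcL and platelets at least 100,000/mcL | Primary, ORR | Yes |
| CRh | <5% | Platelets >50,000/mcL and ANC >500/mcL | Primary | Yes |
| CRi | <5% | ANC <1,000/mcL or platelets <100,000/mcL | Primary; ORR in 9.1.2.1 | No |
| MLFS / marrow CR | <5% | No recovery required | ORR | As mCR, if that means marrow CR |
| PR | 5% to 25%, and at least a 50% decrease | All CR count criteria | ORR | No |

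**Step 2. PR.** CR, CRh and marrow CR all need blasts below 5%; PR needs 5% to 25%. The ranges do not overlap, so a naive patient whose response is PR meets the stopping item however mCR is read.

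**Step 3. CRi.** Take blasts <5%, no circulating blasts or Auer rods, no extramedullary disease, ANC 1,500/mcL and platelets 40,000/mcL. Platelets are below 100,000, so this is CRi. They are not above 50,000, so it is not CRh. Marrow CR requires no blood-count recovery, so the patient also satisfies that definition. If mCR means marrow CR, the patient is not in the absence of mCR.

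The wording still leaves doubt. The term mCR is used in Section 6.3 without definition. Section 9.1.2 uses the phrase modified CR for CR+CRi+CRh, which is a second possible expansion: it would cover CRi but drop MLFS. CR and CRh also satisfy the marrow CR definition, so naming them would be redundant if mCR covered every state with blasts <5%. Sections 9.1.2.1 and 12.1 list CRi and marrow CR separately. A site that records one best category as CRi could read it as unlisted.

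**Step 4. What happens to the endpoints after such a stop.**

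- *Composite CR and ORR:* a documented CRi or PR stays counted, because one occurrence within the six cycles is enough.
- *DOR and PFS:* Section 6.4 provides a 90-day visit and then survival follow-up every 3 months. The Section 11 calendar shows blood counts at the 90-day visit, but no marrow and no response assessment. The assessments otherwise due after later cycles (1, 3, 6, 9 and 12 for naive patients) are not made. The direction of the effect is not fixed: loss of drug could bring progression forward, while loss of assessments could delay or miss its documentation.
- *Primary rate:* a PR stopped before the end of cycle 6 can no longer deepen to CR on olaparib within the window. This depends on when the item is applied. If it is applied only after cycle 6, the primary count is unaffected.

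**Step 5. How sensitive the naive-arm design is to lost conversions.** Inputs from the Section 9.1.1 table: H0 30%, H1 50%; stop if 6 or fewer of 19 respond; success if 17 or more of 39 respond.

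P(success | p) = Σ over x = 7 to 19 of P(X₁ = x) × P(X₂ ≥ 17 − x), with X₁ ~ Bin(19, p) and X₂ ~ Bin(20, p).

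This reproduces the plan: 0.0455 at p = 0.30 (stated 5%) and 0.804 at p = 0.50 (stated 80%).

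Now suppose a share f of eventual composite CRs is lost because patients are stopped before converting, so p = 0.50 × (1 − f). **The values of f are assumptions; the documents give no PR frequency and no conversion rate.**

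| f | p | Power | P(stage-1 futility) |
|---|---|---|---|
| 0 | 0.500 | 0.804 | 0.084 |
| 5% | 0.475 | 0.710 | 0.122 |
| 10% | 0.450 | 0.599 | 0.173 |
| 20% | 0.400 | 0.356 | 0.308 |

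One lost success in 39 is 1/39 = 2.6 percentage points; two are 2/39 = 5.1 points. The table shows that the design is sensitive. It does not estimate the loss.

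**The case against.** A reader might infer that patients in CRi must stop, so that the protocol removes its own primary-endpoint successes. The documents do not support that. Section 9.1.2.1 pairs marrow CR with MLFS, Section 12.1 requires no hematologic recovery for it, and every CRi meets its marrow criteria. The categories are not mutually exclusive: CRi and CRh share a row, and a patient with adequate ANC and platelets of 60,000/mcL is both. This objection stands. For CRi, only ambiguity of labelling remains.

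A reader might also infer that responses are lost from the primary or ORR counts, or that naive and exposed arms become non-comparable. Neither follows. Response is cumulative, so a documented response stays counted. Section 9.3 has the cohorts evaluated independently, and no naive-versus-exposed comparison of ORR, DOR or PFS is planned. The expectation of similar efficacy in Section 9.1.1 is background, not a test.

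Two further objections stand in part. Different handling of naive patients is deliberate, because other approved options exist (Section 2.3); but that section ties the switch to progression, and PR is not progression. The reduced follow-up after the last dose applies whatever the reason for stopping; but here the protocol itself would create the stop, in a responder, and only in arms 1 and 3.

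**Conclusion.** The point holds in limited form. For PR it is a contradiction in the current text: an ORR success in arms 1 or 3 meets a stop for lack of response, against Section 2.3 and alongside a more permissive provision for PD in Section 12.1. For CRi it is an undefined term that could lead some sites to stop a primary-endpoint success.

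The effect falls on DOR and PFS within arms 1 and 3 (up to 39 + 39 = 78 patients by the design table), and only on patients whose response is PR or is labelled CRi. Its size and direction cannot be derived from the documents. An effect on the primary rate is possible only if the item is applied before cycle 6 and some partial responders would have deepened; no figure in the documents allows it to be estimated. The Simon design figures for the naive arms are correct and not in dispute. The correction should be made, because it is cheap and the text is inconsistent as it stands.

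**What to change.** 1. Reconcile the response list in Section 6.3 with Sections 2.3, 9.1.2.1, 9.4.2 and 12.1, including the PD comment in 12.1.
2. Define mCR where it is used, and name CRi explicitly, so that no category counted as a primary-endpoint success also reads as a stop for lack of response.
3. State how PR is treated in naive patients, and at which assessment the item takes effect. The clinical rule is for the sponsor to decide; the need is that the sections agree.
4. If any responder category is still to be stopped by protocol, add to Section 9.4.3 how DOR and PFS handle those patients (event, censoring and date of last assessment), and report their DOR separately.

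The cost is one revised line in Section 6.3, a definition, and a sentence or two in Section 9.4.3. No extra patients or procedures are needed. If the sponsor widens the list, some naive patients may stay on olaparib longer.

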### 6.4 Duration of Follow-Up

Patients will be seen 90 days after the last dose of the study drug for a follow-up visit and then followed for survival q3 months (+/- 4 weeks) thereafter until death. Patients removed from study for unacceptable AE(s) will be

followed until resolution or stabilization of the AE. Survival data will be followed until death from any cause.

## 7. DOSING DELAYS/DOSE MODIFICATIONS

### 7.1 Dose Levels

Any toxicity observed during the course of the study could be managed by interruption of the dose of study treatment or dose reductions. Repeat dose interruptions are allowed as required, for a maximum of 2 weeks of treatment interruption total. If the interruption is any longer, the study team must be informed. Study treatment can be dose reduced to 250 mg twice daily as a first step and to 200 mg twice daily as a second step. If the reduced dose of 200 mg twice daily is not tolerable, no further dose reduction is allowed and study treatment should be discontinued. When dose reduction is necessary patients will take one 150 mg tablet and one 100 mg tablet twice daily or two x 100 mg tablet twice daily, or one 150 mg tablet twice daily or one 100 mg tablet twice daily.

Once dose is reduced, escalation is not permitted (except following concomitant treatment with CYP3A4 inhibitors – see Section 6.2.3).

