## 6. TREATMENT PLAN

### 6.1 Agent Administration

Treatment will be administered on an outpatient basis. Reported AEs and potential risks are described in Section 10. Appropriate dose modifications are described in Section 7. No investigational or commercial agents or therapies other than those described below may be administered with the intent to treat the patient's malignancy.

Regimen Description					
Agent	Premedications / Precautions	Dose	Route	Schedule	Cycle Length
Olaparib	
 
Do not consume grapefruit juice.
 
Olaparib tablets can be taken with or without food.
 
	If CrCl = 30 - 50 mL/min: 200 mg (2 x 100 mg tablets)	Tablet PO q12h	Daily	28 days (4 weeks)
		If CrCl > 50 mL/min: 300 mg (2 x 150 mg tablets)			

PO = oral administration, q12h = every 12 hours

- For patients with CrCl between 30 and 50 mL/min, the starting dose will be 200 mg bid.
- For patients with CrCl > 50 mL/min, the starting dose will be 300 mg bid.

NCI Protocol #: 10264

Version Date: December 11, 2024

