### 7.2 Management of hematological toxicity

Hematologic toxicity will be defined using specific AML/MDS criteria: For patients with documenting response, any CTCAE grade 4 ANC or platelet toxicity lasting >42 days from the initiation of the cycle will be considered a DLT.

In the absence of active disease, study drug should be interrupted until recovery of the hematologic toxicity to  $\leq$  Grade 3 for all subjects regardless of baseline cytopenia. The treatment will then be re-started at the lower dose level as indicated on section 7.1 of the protocol.

The definition and management of hematologic toxicities is complex and we strongly encourage the local investigator to contact the study team to discuss the next steps of management if a hematologic toxicity is suspected.

Note that a complete response with inadequate platelet recovery will not considered a hematologic toxicity.

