#### 7.5 Renal Impairment

If after study entry and while still on study therapy, a patient's estimated CrCl falls below the threshold for study inclusion (>30 ml/min), retesting should be performed promptly.

A dose reduction is recommended for patients who develop moderate renal impairment (calculated creatinine clearance by Cockcroft-Gault equation or based on a 24-hour urine test of between 30 and 50 ml/min) for any reason during the course of the study: the dose of olaparib should be reduced to 200 mg twice daily.

Because the CrCl determination is only an estimate of renal function, in instances where the CrCl falls to between 31 and 50 mL/min, the investigator should use his or her discretion in determining whether a dose change, or discontinuation of therapy is warranted.

Olaparib has not been studied in patients with severe renal impairment (CrCl ≤ 30 mL/min) or end-stage renal disease; if patients develop severe impairment or end stage disease it is recommended that olaparib be discontinued.

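### The dose-modification rules conflict for patients at 200 mg twice daily, and Section 7.5 gives two rules for CrCl 31 to 50 mL/min

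*Combined protocol and SAP*

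**What the plan says.** **The floor.** Section 7.1 describes a ladder from 300 mg to 250 mg to 200 mg twice daily and then says: "If the reduced dose of 200 mg twice daily is not tolerable, no further dose reduction is allowed and study treatment should be discontinued". The next sentence lists tablet combinations for use when a reduction is needed. After the 250 mg and 200 mg combinations it ends with "or one 150 mg tablet twice daily or one 100 mg tablet twice daily", and attaches no condition to those two.

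**Starting at the floor.** Section 6.1: "For patients with CrCl between 30 and 50 mL/min, the starting dose will be 200 mg bid". The reduction tables that follow Sections 7.1, 7.2 and 7.4 each have a single row, beginning at 300 mg.

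**Restart after hematologic toxicity.** Section 7.2 interrupts treatment until recovery to Grade 3 or better, then says: "The treatment will then be re-started at the lower dose level as indicated on section 7.1 of the protocol".

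**CYP3A inhibitors.** Section 6.2.3 says, for strong inhibitors, "reduce the dose of olaparib to 100 mg twice daily for the duration of concomitant therapy with the strong inhibitor" and, for moderate ones, "reduce the dose of olaparib to 150 mg twice daily for the duration of concomitant therapy with the moderate inhibitor". The table in Section 7.6 repeats both doses.

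**Renal function.** Section 7.5 recommends a reduction when CrCl falls to between 30 and 50 mL/min on study: "the dose of olaparib should be reduced to 200 mg twice daily". Its next paragraph, for 31 to 50 mL/min, says "the investigator should use his or her discretion in determining whether a dose change, or discontinuation of therapy is warranted".

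**Hold rule.** Section 9.1.3 counts a grade 4 neutrophil or platelet toxicity, without active disease, when treatment cannot resume within 42 days of the start of the cycle. It holds enrollment at 2 or more such patients among the first 10. It does not mention patients taken off because no lower dose is available.

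**The concern.** A site that follows Section 7.2 for a patient at 200 mg is sent to Section 7.1 for the next level down. There it finds a statement that none exists and, one sentence later, two lower doses. Section 7.1 also calls 200 mg a reduced dose, so it does not speak directly about a patient who began there. The same patient could be taken off, given a lower dose or kept at 200 mg, depending on which sentence the site applies. Section 7.5 leaves similar room for a patient whose renal function declines.

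What is at stake first is consistent and safe dosing across many sites. A secondary stake, for patients at 200 mg only, is the toxicity tally: whether treatment can be restarted depends partly on whether the protocol provides a dose to restart at.

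**Working it through.** The plan gives no figure on this point, so the check is mainly a comparison of passages.

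**Step 1. A patient at 200 mg whose counts have recovered after grade 4 toxicity, without active disease.**

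| Source | What it gives |
|---|---|
| 7.2 text | Restart one level down, as set out in 7.1 |
| 7.1, floor sentence | No lower level; stop if 200 mg is not tolerated |
| 7.1, tablet sentence | 150 mg or 100 mg twice daily are listed |
| Tables after 7.1, 7.2 and 7.4 | No row for a 200 mg start; the last step is 200 mg |

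These do not combine into one instruction. The gap is plainest for patients who start at 200 mg under Section 6.1, because the ladder has no step for them.

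**Step 2. Where the 150 mg and 100 mg tablets may come from.** They equal the moderate- and strong-inhibitor doses in Sections 6.2.3 and 7.6. Section 7.1 does point to 6.2.3, but only in its following sentence, which concerns re-escalation. The link is plausible but not stated.

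**Step 3. Renal function.**

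| CrCl (mL/min) | 3.1.15 | 6.1 (start) | 7.5 (on study) |
|---|---|---|---|
| Exactly 30 | Not eligible (must exceed 30) | 200 mg | In the reduction range and also in the range where stopping is recommended |
| 31 to 50 | Eligible | 200 mg | Reduction to 200 mg recommended, then left to discretion |

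Nothing in 7.5 says which of its two paragraphs governs at 31 to 50. The disagreement over bounds matters only at about 30.

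**Step 4. The hold rule, for patients at 200 mg.** Suppose, as an illustration, that the patient in Step 1 recovers to Grade 3 by day 30 of the cycle.

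- Section 7.2 defines the dose-limiting event by duration beyond 42 days. Recovery at day 30 is not such an event.
- If the site stops treatment at the floor, treatment has not resumed by day 42. Section 9.1.3 could be read as counting this patient, because no restart is allowed. It could also be read as not counting the patient, because the toxicity has resolved.
- If the site uses a dose from the tablet sentence, treatment resumes before day 42 and nothing is counted.

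**Step 5. How much one event can matter.** The hold boundaries are 2/10, 3/15, 4/20, 5/25, 6/30 and 7/35, each exactly 20% at the top of its band. Take 10 patients and a true event rate of 20%, the stated maximum:

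- P(at least 2 events) = 1 − 0.8^10 − 10 × 0.2 × 0.8^9 = 1 − 0.1074 − 0.2684 = 0.624.
- If one event goes uncounted, 3 true events are needed. P(at least 3) = 0.6242 − 45 × 0.2² × 0.8^8 = 0.6242 − 0.3020 = 0.322.

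This shows how sensitive the rule is to a single classification. It does not estimate how often the dosing text would cause one. The limit also applies within each arm, and the two IDH-inhibitor-exposed arms plan only 14 and 12 patients before drop-out.

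**The case against.** **The lower tablets are loose drafting.** The 200 mg end of the ladder appears in the text of 7.1, again in 7.3 and in three tables, and the 150 mg and 100 mg doses match the inhibitor rule. A reader might infer that the protocol contains two rival toxicity ladders. The documents do not support that, and an unqualified sentence is the likelier explanation. It still needs its condition written in, because 7.2 sends sites to that section.

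**Section 7.2 imports the floor.** It refers to the levels in 7.1, so it can be read as importing the rule on stopping too, and it strongly encourages contact with the study team. That is fair, but contact is not a rule, and neither section provides for a patient who starts at 200 mg.

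**Section 7.5 is a recommendation followed by discretion.** It gives a reason: CrCl is only an estimate. The two paragraphs can be read together, so this limb is an unreconciled ambiguity more than a flat contradiction.

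**The toxicity count is inference.** Section 7.2's definition by duration does not depend on the dose available. This largely stands: the effect arises only through the restart wording in 9.1.3. A reader might extend it to renal dose changes. The documents show no such link, since a renal reduction is not itself a countable event. And any rule set at 2 in 10 is sensitive to one event.

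**Conclusion.** The conflict holds for patients at 200 mg twice daily, whether they were reduced to that dose or started there: the protocol does not give one instruction after hematologic toxicity. The two paragraphs of Section 7.5 and the CrCl bounds at 30 mL/min also need reconciling, as a lesser point. The effect on the hold rule is secondary, is confined to patients at 200 mg, and depends on how 9.1.3 is read.

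No stated sample size, alpha or power changes. The number of patients affected cannot be derived from the documents. A reader might apply an assumed share to the 104 patients obtained by adding the arms (39 + 14 + 39 + 12; the text states 94). The share starting at 200 mg is not given, and such a count would include every 200 mg starter rather than those who go on to need a reduction. The probabilities in Step 5 of the working assume a 20% event rate and a single look at 10 patients, and are illustrative. The point is worth correcting because it concerns safety and costs little.

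**What to change.** The sponsor should reconcile Sections 3.1.15, 6.1, 6.2.3, 7.1, 7.2, 7.5 and 7.6 and the dose tables:

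- State one rule for patients who are at, or start at, 200 mg twice daily, and show it in the tables, whatever that rule is.
- Say whether the 150 mg and 100 mg tablets in 7.1 refer only to use with CYP3A inhibitors.
- Keep one rule in 7.5 for CrCl 31 to 50 mL/min, and one set of CrCl bounds throughout.
- State in 9.1.3, consistently with 7.2, whether stopping at the dose floor after count recovery counts towards the hold rule.

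Which dose or rule applies is the sponsor's clinical decision. The cost is amendment wording, with no added patients or procedures.
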